## **9.2 SETTING**

**Study Period:** the entire time period that includes the look-back period, the cohort entry date (drug index date), and follow-up period for the study population. The study period will be from April 18th, 2011 (start of data collection) to December 31st, 2020 (end of data collection).

**Patient Selection Period:** the time period for which patients are eligible to enter the cohort, which is from April 18th, 2012 to December 31st, 2020.

**Cohort Entry Date:** The drug index date, defined as the first date of prescription for dabigatran, rivaroxaban, or warfarin during the patient selection period.

**Look-back Period:** the 365-day period that ends 1 day prior to the cohort entry date. The earliest start date of the look-back period is April 18th, 2011.

**Loss of follow-up:** the last data point available in the database during the study period.

**Follow-Up Period:** the period starting from the cohort entry date (first prescription of the drug of interest) and ending at the earliest occurrence of the following:

- Discontinuation of the index OAC, defined as a continuous gap of 45 days or more between the expected refill date and the actual refill date (discontinuation date defined as 45 days after the expected refill date)
- Switching to another OAC, if the index OAC is discontinued and another OAC is started within 45 days of the expected refill date of the index OAC
- Loss of follow-up
- Occurrence of outcomes of interest (for primary outcome: major bleeding; for secondary outcome: the onset of the first occurring component event; for further outcomes: the respective onset of component events)
- Death (except for analyses for the composite outcome and all-cause mortality as a component outcome)
- End of study period

The notion of enrollment is not defined in [REDACTED]. Therefore, a proxy enrolment criterion defined as start of enrolment = date of first inpatient/outpatient encounter; end of enrolment = date of last inpatient/outpatient encounter will be used. "Enrolment" herein will refer to this proxy enrolment measure. For entry into the study population, patients will be required to have had at least 365 days of enrollment prior to the cohort entry date.

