### **9.3.2 Outcomes**

Outcomes are recorded with the 10th Revision of the International Classification of Diseases (ICD-10) codes. In the [REDACTED] database, information related to outcomes include the date of occurrence, the number of events, and the severity. All outcomes are incident events after the index date.

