**Comorbidities (has at least 1 diagnosis before or on the index date during the look-back period)**

- Heart failure (yes/no)
- Peripheral arterial disorder (yes/no)
- Hypertension (yes/no)
- Diabetes (yes/no)
- Prior stroke/transient ischemic attack (TIA)/SE (yes/no)
- Cerebrovascular disease (yes/no)
- Myocardial infarction (yes/no)
- Acute Coronary Syndrome (yes/no)
- Unstable angina (yes/no)
- Bleeding history (yes/no)
- Renal dysfunction (yes/no)
- Hepatic dysfunction (yes/no)
- Cancers (yes/no)
- Peptic ulcer disease (yes/no)
- Obesity (yes/no)

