#### **7.2.1 Follow up period**

The follow up period starts from cohort entry date (first prescription of the drug of interest) and ends at the earliest date of the following dates:

- Discontinuation date of index OAC.

Proprietary confidential information © 2022 Boehringer Ingelheim International GmbH or one or more of its affiliated companies

Discontinuation of the index OAC, defined as a continuous gap of 45 days or more between the expected refill date and the actual refill date. The discontinuation date is defined as 45 days after the expected refill date. The codes for index OAC are listed in [Annex 1](#).

- Date of switching to another OAC.  
If the index OAC is discontinued, the date of switching to another OAC was the first prescription date of another OAC within 45 days of the expected refill date of the index OAC. The codes of another OAC are the codes in [Annex 1](#) excluding codes of the index OAC.
- Loss of follow-up date.  
The date of the last inpatient/outpatient encounter during period starting from index OAC date and ending on December 31st, 2020.
- Date of the first occurrence of outcomes of interest (for primary outcome: major bleeding; for secondary outcome: the onset of the first occurring component event; for further outcomes: the respective onset of component events) during period starting from index OAC date and ending on December 31st, 2020.
- Date of death during period starting from index OAC date and ending on December 31st, 2020.
- End of study period date (December 31st, 2020).

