### **8.2 OUTCOMES**

#### **8.2.1 Primary outcomes**

Operational definition of fatal or non-fatal major bleeding is the first new confirmed diagnosis of

- blood transfusion (inpatient or outpatient)  
OR
- bleeding of inpatient (non-DPC hospital)  
OR
- bleeding of inpatient (DPC hospital) with “disease name behind this hospitalization” (“dpcdiseasesegment”=21)

during the follow up period. The ICD-10 diagnosis codes of blood transfusion and bleeding are in [Annex 3](#).

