### **8.3 COVARIATES**

Please check section 9.3.3. of the study protocol. List of covariates and operational definitions are added to [Annex 4](#).

The HAS-BLED score is calculated as the total points of the following elements (1 point per element) during the baseline period including the index date.

- Confirmed diagnosis of hypertension
- Dialysis-dependent kidney disease including confirmed diagnosis of hepatic dysfunction or confirmed diagnosis of renal dysfunction or on hemodialysis treatment
  - OR
- Confirmed diagnosis of cirrhosis
  - OR
- Renal transplant
  - OR
- Serum creatinine > 200 m mol/L
  - OR
- ALP > 3x upper limit (1050 IU/L) or ALT > 3x upper limit (132 IU/L) or AST > 3x upper limit (114 IU/L)
  - OR
- Bilirubin > 2x upper limit (2.4 mg/dL)
- Confirmed diagnosis of stroke
- Confirmed diagnosis of bleeding history
- Age calculated as of index date > 65 years old
- Confirmed diagnosis of excessive alcohol use
  - OR
- on treatment of excessive alcohol use
  - OR
- on antiplatelet drugs or non-steroidal anti-inflammatory drug

The CHA2DS2-VASc score is calculated as the total points of the following elements during the baseline period including the index date.

- Confirmed diagnosis of congestive heart failure (1 point)
- Hypertension (1 point) including confirmed diagnosis of hypertension or on any anti-hypertensive medications
- Age calculated as of index date  $\geq$  75 years old (2 points)

---

Proprietary confidential information © 2022 Boehringer Ingelheim International GmbH or one or more of its affiliated companies

- Diabetes Mellitus (1 point) including confirmed diagnosis of diabetes mellitus or on any anti-hyperglycemia agents or on any insulin treatment
- Confirmed diagnosis of stroke (2 points)
- Vascular disease including confirmed diagnoses of MI or peripheral arterial disorder (1 point)
- Age between 65 and 74 (1 point)
- Female (1 point)

The code used to define the elements of HAS-BLED score and CHA2DS2-VASc score are in [Annex 4](#).

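### The SAP counts outcomes from the index date, the protocol only after it, so a same-day diagnosis can be both a baseline risk element and an outcome event

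*SAP*

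**What the plan says.** **Outcome window.** Protocol 9.3.2 states: "All outcomes are incident events after the index date". SAP 7.2.1 ends follow-up at the first outcome found "during period starting from index OAC date and ending on December 31st, 2020". SAP 8.2.1 begins: "Operational definition of fatal or non-fatal major bleeding is the first new confirmed diagnosis of", and goes on to list transfusion and inpatient bleeding, counted during follow-up. SAP 8.2.2 has the same structure for the composite. Neither defines *new* or excludes the index date.

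**Start of follow-up.** Protocol 9.2 and SAP 7.2.1 both start follow-up on the cohort entry date, which is the index date. SAP section 8 refers the reader back to protocol 9.3 for the study variables.

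**Baseline window.** SAP 8.3 scores HAS-BLED and CHA2DS2-VASc "during the baseline period including the index date". Protocol 9.3.3 defines a comorbidity as present if the patient "has at least 1 diagnosis before or on the index date during the look-back period", but protocol 9.2 and SAP 7.2 end the look-back period one day before cohort entry. Under SAP 11.1, all Annex 4 covariates except two antiplatelet variables enter the generalized propensity score (GPS). Both scores are therefore in the model.

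**The concern.** Outcomes and baseline risk should not share a day unless a rule says which role a diagnosis takes. Here the dates overlap and there is no such rule. A bleed, stroke or MI recorded on the day the anticoagulant is first prescribed may be the reason for the visit or part of the reason for the prescription. Under SAP 7.2.1 and 8.2 it can still be counted as an event on the drug. The same diagnosis can feed the weights through the risk scores, so weighting cannot be relied on to remove the problem.

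This affects the primary hazard ratio (major bleeding) and the secondary one (net clinical benefit). The two visible sensitivity analyses would not reveal it. Propensity score matching (protocol abstract) and restriction to 3 years of follow-up (SAP 11.1) do not change the starting day.

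**Working it through.** The plan states no figure on this point, so the main check compares the texts. The arithmetic only illustrates size.

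**1. How each rule treats a diagnosis dated on the index date**

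| Rule | Place | Day 0 |
|---|---|---|
| Outcomes | Protocol 9.3.2 | excluded |
| Outcomes | SAP 7.2.1 | included |
| Outcome definitions | SAP 8.2.1, 8.2.2 | not excluded; *new* undefined |
| Start of follow-up | Protocol 9.2, SAP 7.2.1 | included |
| HAS-BLED, CHA2DS2-VASc | SAP 8.3 | included |
| Separate comorbidities | Protocol 9.3.3 with 9.2 | self-contradictory |

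**2. One case followed through.** Take a stroke first recorded on day 0. It adds 1 point to HAS-BLED and 2 to CHA2DS2-VASc, and both scores enter the GPS. It also falls inside the SAP outcome window and, being first recorded that day, can be read as new, so it is a composite event at time 0. The same holds for a bleed (a HAS-BLED element and potentially the primary outcome) and for an MI (an element of CHA2DS2-VASc and of the composite). An MI may even confer eligibility: inclusion criterion 5 accepts a CAD diagnosis on the index date, and Annex 2 lists acute MI under CAD. The code lists for the score elements, the comorbidities and the stroke and MI outcomes are in attachments not shown, so overlap code by code cannot be checked.

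**3. Share of events in the dabigatran arm**

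Inputs from protocol 9.5: about 4,000 dabigatran users, 3 events per 100 patient-years, 1 year of exposure, and a longest mean treatment duration of 868 days (dabigatran) in a published cohort. Assumption: 0.2–0.5% of patients have a day-0 event, in addition to the planned rate.

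- Day-0 events: 4,000 × 0.002 = 8; 4,000 × 0.005 = 20.
- Over 1 year: 4,000 × 0.03 = 120 later events. Share = 8/128 = 6% to 20/140 = 14%.
- Over 868 days (868/365.25 = 2.376 years): 4,000 × 0.03 × 2.376 = 285 later events. Share = 8/293 = 3% to 20/305 = 7%.

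**4. Effect on the ratio if both arms have the same day-0 share**

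The plan's dabigatran total is reproduced first, to see how it uses the rate. Schoenfeld events at HR 0.66, two-sided 5%, 80% power, 1:1: 4 × (1.960 + 0.842)² / (ln 0.66)² ≈ 182. Then 182/0.03 = 6,067, against 6,050 in the protocol. The 3 per 100 thus acts as the average rate of the two arms.

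With that average and a true ratio of 0.66, the warfarin risk over one year is r0 = 2 × 0.03/(1 + 0.66) = 0.0361 and the dabigatran risk is r1 = 0.66 × r0 = 0.0239. Adding a day-0 share q to both arms gives an observed ratio of (q + r1)/(q + r0):

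| q (assumed) | Day-0 share of all events, q/(q + 0.03) | Observed ratio |
|---|---|---|
| 0.1% | 3% | 0.67 |
| 0.25% | 8% | 0.68 |
| 0.5% | 14% | 0.70 |
| 1% | 25% | 0.73 |

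These are crude one-year ratios, not weighted hazard ratios. Equal shares pull the ratio toward 1. If the share differs by drug, the bias can go either way.

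**The case against.** The strongest reply is that the SAP never revokes the protocol rule. SAP section 8 points to protocol 9.3, which contains the restriction to incident events after the index date. The SAP 7.2.1 wording also closes the loss-to-follow-up and death items, so it may only bound a search for end dates. The protocol's own follow-up starts on day 0 too, and *new*, read together with *incident*, could exclude a diagnosis already counted at baseline.

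Much of this is fair. A reader might infer that the SAP deliberately overrides the protocol; the documents do not show that. They show two inconsistent rules, with a looseness already present between protocol 9.2 and 9.3.2. But a general pointer does not tell a programmer which rule to apply, and an undefined *new* does not settle a diagnosis first recorded on day 0. Starting person-time on day 0 is compatible with counting outcomes from day 1, so protocol 9.2 does not require day-0 events to count.

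Three stronger readings should be resisted:

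- That every day-0 event is reverse causation. An event can follow the first dose on the same day; the data carry dates, and the plan has no rule for order within a day.
- That a day-0 anaemia code also enters the propensity model. Anaemia appears in the Annex 3 outcome codes but in no visible covariate list.
- That in-hospital starters carry many such codes, or that their share differs by drug. The documents give no data on either.

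The comorbidity wording is weaker support than the two scores, because it conflicts with a look-back ending the day before. The overlap rests on the scores.

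**Conclusion.** The inconsistency is certain from the text; its effect is not known. Followed as written, the SAP can count as on-drug events diagnoses that protocol 9.3.2 excludes, and the same diagnoses can raise the baseline scores used for weighting.

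The size rests on an assumed day-0 frequency that has no source in the documents. Under that assumption the effect ranges from small to moderate, and it depends on the planning rate and on exposure time. Bias in the study's hazard ratios is therefore possible but not established. The point should be settled before results are seen, because two programmers following these documents could produce different primary event counts.

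**What to change.** In SAP 7.2.1 and 8.2:

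- count outcomes only from the day after the index date, in line with protocol 9.3.2;
- treat diagnoses dated on the index date as baseline only;
- define *new* to match;
- report the number of day-0 outcome codes by treatment group, so that the size is known rather than assumed.

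The comorbidity window should be reconciled with the look-back definition at the same time, by stating whether day 0 belongs to it.

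Diagnoses belonging to an admission already under way at the index date are a further matter. Excluding them goes beyond protocol 9.3.2 and would need linkage to admissions, so it fits best as an optional sensitivity analysis.

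The core change costs one SAP sentence, one programming condition and a small loss of events (8–20 in the dabigatran arm under the assumption above).

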### **7.3 STUDY POPULATION**

The target population of the study are Japanese NVAF patients with concomitant CAD, who are prescribed with dabigatran, rivaroxaban, or warfarin. The study population will be selected based on the following in/exclusion criteria:

#### **Inclusion Criteria**

1.  $\geq 18$  years of age on index date
2. Has one year of look-back period prior to the index date (defined as the first date of prescription for dabigatran, rivaroxaban, or warfarin during the study period)
3. New users of warfarin, dabigatran, and rivaroxaban, defined as patients without historic use of any oral anticoagulants during the look-back period
4. Has at least 1 diagnosis of NVAF during the look-back period prior to or on the index date
5. Has at least 1 diagnosis of CAD during the look-back period prior to or on the index date

#### **Exclusion Criteria**

1. Diagnosed with end-stage renal disease (ESRD), or undergo hemodialysis, or experience pregnancy during the study period
2. Initiate warfarin, dabigatran, rivaroxaban due to valvular AF (VAF), AF associated with mechanical valve malfunction or mechanical complication of heart valve prosthesis, or rheumatic AF
3. Underwent joint replacement procedures or diagnosed with venous thromboembolism during the look-back period prior to or on the index date
4. Prescribed with more than 1 OAC on the index date

---

Proprietary confidential information © 2022 Boehringer Ingelheim International GmbH or one or more of its affiliated companies

5. Prescribed with more than 2 anti-platelet drugs per prescription (triple or quadruple anti-platelet use), or prescribed with any anti-platelet injection
6. Patients with missing or ambiguous age or sex information

The codes for OAC are listed in [Annex 1](#) and codes to select study population (in/exclusion criteria) are listed in [Annex 2](#).

NVAF during the look-back period prior to or on the index date is defined as patients had diagnosis of AF and had no diagnosis of VAF during the specific period.

Pregnancy during the study period is defined as patients had any of the following:

- Confirmed diagnosis of pregnancy in the study period.
- In FF1 data (discharge summary data), the admission date was within the study period, and returned true for the pregnancy flag or the number of weeks of pregnancy at the time of hospitalization greater than 0 or the number of weeks of pregnancy at the time of delivery greater than 0.
- Medical treatment of pregnancy in the study period.

AF associated with mechanical valve malfunction or mechanical complication of heart valve prosthesis is defined as a record with diagnosis of AF and diagnosis of mechanical valve malfunction or mechanical complication of heart valve prosthesis.

Rheumatic AF is defined as a record with diagnosis of AF and diagnosis of rheumatic heart disease.

#### **7.4            STUDY VISITS**

Not applicable.

## **8. VARIABLES**

Study variables are explained the study protocol section 9.3. you can find operational definitions below:

### **8.1 EXPOSURES**

Respectively for Group 1 (new users of warfarin), group 2 (new users of dabigatran), and group 3 (new users of rivaroxaban), the first prescribed dates of warfarin, dabigatran and rivaroxaban during the study period were selected as the index date, and the patients did not have any OAC prescription during the look back period. The [REDACTED] Receipt Code of warfarin, dabigatran and rivaroxaban are in [Annex 1](#).

### **8.2 OUTCOMES**

#### **8.2.1 Primary outcomes**

Operational definition of fatal or non-fatal major bleeding is the first new confirmed diagnosis of

- blood transfusion (inpatient or outpatient)  
OR
- bleeding of inpatient (non-DPC hospital)  
OR
- bleeding of inpatient (DPC hospital) with “disease name behind this hospitalization” (“dpcdiseasesegment”=21)

during the follow up period. The ICD-10 diagnosis codes of blood transfusion and bleeding are in [Annex 3](#).

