##### **Primary outcome:**

- Fatal or non-fatal major bleeding (defined as any blood transfusion and/or any hospitalization with associated bleeding) in all three patient groups

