### **11.1 MAIN ANALYSIS**

During the first step of the comparative analysis, the baseline characteristics of the individual NOAC groups will be balanced with the warfarin group to account for potential confounding effects through an inverse probability of treatment weighting (IPTW) method. A multinomial logistic regression model will be used to estimate the generalized propensity score (GPS). The treatment membership (warfarin, dabigatran and rivaroxaban) is the dependent variable and all the covariate variables listed in [Annex 4](#) except for “Anti-platelet drugs” and “The number of anti-platelet drugs per prescription” are independent variables in the multinomial logistic regression model, as the two variables can be fully derived from the variable “Anti-platelet use duration”. For each patient, we will obtain the estimated GPS vector with components of the probabilities of receiving each treatment (warfarin, dabigatran and rivaroxaban) through the multinomial logistic regression model.

The stabilized IPTW (s-IPTW) will be used to deal with the inflation of type I error and extremely large weight when using regular IPTW. The s-IPTW is calculated as

$$w_i = \frac{\Pr(T = k)}{\Pr(T = k|X = x_i)}$$

for the  $i$ th patient, where  $T$  is the treatment membership and  $x_i$  is the covariates of this patient. The denominator is the  $k$ th component of GPS vector of the  $i$ th patient who was actually in treatment group  $k$  and the numerator is the marginal probability of receiving treatment  $k$  [\[R22-1420\]](#).

The GPS distributions (density curves, boxplots) of each treatment will be used to examine GPS overlap between the treatment groups. Patients outside of the common support or overlap area for any component of the GPS vector are removed from the analysis. The area of common support is formed by defining boundaries for each component  $k$ ,  $k = 1, 2, 3$  of the GPS vector [\[R22-1419\]](#):

$$\Pr(T = k|x)^{low} = \max[\min(\Pr(T = k|x, T = 1)), \min(\Pr(T = k|x, T = 2)), \min(\Pr(T = k|x, T = 3))]$$

$$\Pr(T = k|x)^{high} = \min[\max(\Pr(T = k|x, T = 1)), \max(\Pr(T = k|x, T = 2)), \max(\Pr(T = k|x, T = 3))]$$

[figure not shown]
The distributions of s-IPTW for each treatment group will be examined, the mean s-IPTW is expected to be close to 1. Weight truncation based on the distributions of s-IPTW will be applied if there are extremely high s-IPTW.

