Proprietary confidential information © 2022 Boehringer Ingelheim International GmbH or one or more of its affiliated companies

The baseline demographics, risk factors, and clinical characteristics will be compared between the treatment groups (dabigatran vs warfarin, rivaroxaban vs warfarin, dabigatran vs rivaroxaban) using the absolute standardized difference (ASD) pre- and post- s-IPTW to assess the balance of these confounders. A covariate will be considered well balanced if the ASD is below 0.1.

A Cox proportional hazard regression model with s-IPTW will be used to estimate adjusted hazard ratios (aHRs) of treatments (dabigatran vs warfarin, rivaroxaban vs warfarin) and their 95% CIs on primary, secondary, and further outcomes. The treatment membership is the independent variable in the model. A patient will be censored if discontinuation of the index OAC or switching to another OAC or death or loss to follow-up occurred before outcome event. If substantial covariate imbalance between treatment group is noted assessed by a standardized difference  $>0.1$ , then the Cox proportional hazard model will be further adjusted by including covariates that are out of balance in the model. A robust sandwich variance estimation of the treatment effect estimates will be used to account for the fact that the pseudo-population size is inflated or deflated relative to the original population and that weights are estimated [\[P21-02302\]](#).

A sensitivity analysis will be performed by restricting the follow-up period to 3 years for Cox regression models on primary and secondary outcomes.

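### Inpatient bleeding is counted by a wider rule in non-DPC than in DPC hospitals, and no visible analysis checks or adjusts for hospital type

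*SAP*

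**What the plan says.** Protocol 9.3.2.1 gives one definition of major bleeding for every patient: "defined as any blood transfusion and/or any hospitalization with associated bleeding". It does not mention hospital type.

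SAP 8.2.1 turns this into three branches, each needing a first new confirmed diagnosis during follow-up:

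- "blood transfusion (inpatient or outpatient"), whatever the hospital type;
- "bleeding of inpatient (non-DPC hospital"), with no further condition;
- "bleeding of inpatient (DPC hospital) with" the field dpcdiseasesegment equal to 21, meaning that the bleed is coded as the condition behind that admission.

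SAP 8.2.2 applies the same DPC/non-DPC split to major GI bleeding, and takes major bleeding as defined above into the composite.

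For confounding control, SAP 11.1 builds the generalized propensity score from "all the covariate variables listed in" Annex 4, apart from two antiplatelet variables that can be derived from a third. Annex 4 covers demographics, risk scores, comorbidities, co-medications and procedures. Neither Annex 4, Protocol 9.3.3 nor the Table 2a shell contains a hospital variable. For the weighted Cox model, SAP 11.1 states: "The treatment membership is the independent variable in the model". Further terms enter only under the rule that begins "If substantial covariate imbalance between treatment group is noted assessed by a standardized difference" above 0.1.

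**The concern.** Take a patient admitted for another reason who has a new, confirmed bleeding code recorded during the stay, without transfusion. That patient is a primary event in a non-DPC hospital and a non-event in a DPC hospital. The recorded rate can therefore depend on where the patient is treated, apart from any drug effect.

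This does no harm to the comparison if the arms have the same hospital mix. If they do not, part of the ascertainment difference passes into the hazard ratio. The patient-level covariates remove it only so far as they happen to predict hospital type. The plan's safety net cannot catch it either: a variable that is not in the balance table cannot show a standardized difference above 0.1. At stake are the primary hazard ratios for dabigatran and rivaroxaban against warfarin, and the composite that contains the same events.

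**Working it through.** **The plan's own figure.** The documents give no figure on hospital type. The nearest stated figure is the sample size in Protocol 9.5 for dabigatran against warfarin. With hazard ratio 0.66, 80% power, 1:1 allocation and two-sided 5% (assumed from the 95% intervals, as alpha is not stated), the Schoenfeld formula gives 4 × (1.96 + 0.842)² / (ln 0.66)² = 182 events. At 3 per 100 patient-years and one year of exposure, 182 / 0.03 = 6,067, against 6,050 stated. At 4.5 per 100, 182 / 0.045 = 4,044, against 4,040 stated. The stated sizes reproduce, so the same rate and exposure are used below to judge scale.

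**The bias factor.** Let R be the ratio of recorded major-bleeding rates, non-DPC to DPC, taken as equal in both arms and covering all branches including transfusion. Let q_N and q_W be the shares of NOAC and warfarin patients in non-DPC hospitals after weighting. For a rare event with the same true hazard ratio in both hospital types,

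observed HR = true HR × [1 + q_N(R − 1)] / [1 + q_W(R − 1)].

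R, q_N and q_W are not in the documents. The values below are assumptions chosen to show a range.

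| R | q_N 10%, q_W 20% | equal shares | q_N 20%, q_W 10% |
|---|---|---|---|
| 1.25 | 1.025/1.050 = 0.976 | 1.00 | 1.024 |
| 1.5 | 1.05/1.10 = 0.955 | 1.00 | 1.048 |
| 2 | 1.10/1.20 = 0.917 | 1.00 | 1.091 |

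At R = 2, the planning hazard ratio of 0.66 would be recorded as 0.605 or 0.72, and 0.74 as 0.678 or 0.807, depending on which arm has the larger non-DPC share.

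**Effect on a null comparison.** Protocol 9.5 gives roughly 4,000 dabigatran, 11,000 rivaroxaban and 17,000 warfarin patients. At 3 per 100 patient-years for one year, expected events are 0.03 × 21,000 = 630 for dabigatran against warfarin and 0.03 × 28,000 = 840 for rivaroxaban against warfarin. The shift in the test statistic is √[D p(1 − p)] × |ln factor|, where D is the number of events and p the NOAC fraction. With R = 2 and shares of 10% against 20%:

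- dabigatran: √(630 × 0.190 × 0.810) × 0.087 = 0.86, a two-sided false-positive rate of about 14%;
- rivaroxaban: √(840 × 0.393 × 0.607) × 0.087 = 1.23, about 23%.

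At R = 1.25 with the same shares, both are about 6%. These figures ignore the information lost through weighting.

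**Simulation check.** Twelve simulated data sets of 40,000 patients per arm used R = 2 and a deliberately larger imbalance, 10% NOAC against 30% warfarin. The formula gives 1.10/1.30 = 0.846.

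| True HR | Cox without hospital type | Cox stratified by hospital type |
|---|---|---|
| 1.00 | 0.846 (SE 0.008) | 0.993 (SE 0.011) |
| 0.66 | 0.553 (SE 0.005) | 0.654 (SE 0.005) |

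The formula holds, and stratification removes the bias within simulation error. Each simulated patient has one hospital type throughout, so this is the favourable case for the fix.

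**The case against.** The strongest reply is that nothing in the documents shows a bias. Protocol 9.4 says only that the data come from over 400 acute care hospitals. The non-DPC share could be close to zero or the same in all arms, and in either case the factor is essentially 1.00. This stands, and it makes the point conditional.

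Three further replies stand in part.

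- The rules differ less than they first appear to. Every branch needs a new confirmed diagnosis, the transfusion branch is common to both hospital types, and no separate bleeding code list is given for each type. Minor bleeds therefore do not by themselves separate the two. What separates them is bleeding that was not the reason for admission. The common branch pulls R towards 1 by an amount that cannot be determined.
- The split probably follows the data structure, since the name of the filtering field suggests that it exists only for DPC records. The non-DPC branch is also the closer of the two to the protocol's wording. That explains the rule but does not make recorded rates comparable across hospitals.
- Sections between SAP 11.1 and 11.3, and between Protocol 9.7.1 and 9.7.3, are redacted and may contain a DPC-only sensitivity analysis. The main model and its covariate list are visible, however, and hospital type is in neither. The visible sensitivity analyses (1:1 propensity score matching in the protocol abstract and three-year follow-up in SAP 11.1) are not described as using hospital type.

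The ENCePP checklist answers on stratification and outcome misclassification add little. They describe the protocol, which does not contain the split.

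**Conclusion.** The documents establish that the inpatient bleeding rule is wider in non-DPC hospitals, and that hospital type is absent from the propensity model, the balance table shown and the Cox model. The primary and composite hazard ratios are therefore open to bias if the non-DPC share differs between arms after weighting.

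A reader might infer that the hazard ratio is biased, or biased in favour of the NOACs. The documents support neither, because they give no hospital mix by drug and no ascertainment ratio, and reversing the shares reverses the direction.

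For the primary outcome, with R assumed between 1.25 and 2 and shares of 10% and 20% in either order, the factor runs from about 0.92 to 1.09. At the low end of R this is negligible. At R = 2 it would matter for a comparison near the null. The stroke, MI and mortality components of the composite do not carry the split, so they would dilute the effect there. This is an inexpensive safeguard worth adding, not a demonstrated error in the result.

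**What to change.** 1. Derive the DPC/non-DPC status of the hospital issuing the index prescription, and report its distribution by arm before and after weighting. If the shares agree, the concern is largely answered.
2. Add this variable to the Annex 4 covariates used in the propensity model and to the balance table, or stratify the weighted Cox models for the primary and composite outcomes by it.
3. Report a sensitivity analysis of the primary outcome restricted to DPC hospitals, where one definition applies. State whether the restriction applies to the index hospital, to the hospital recording the bleed, or to both.

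The third item is needed because index status is only a proxy. SAP 8.2.1 uses the type of the hospital that records the bleed. Protocol 9.9 says the data are not a closed system, and neither document says that a bleed is recorded where the drug was started. Where the two hospitals differ in type, some misclassification remains after the second item.

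The cost is one derived variable built on information the outcome rule already uses, a small loss of precision in the main models, and a smaller sample in the DPC-only analysis.
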